The immune system in the gut actively induces an immune tolerant state to the proteins that are normally consumed. Food allergy occurs when the body has a break in this tolerance, which results in an abnormal immune reaction to food. Peanut allergy is an immunoglobulin E (IgE)-mediated hypersensitivity reaction following the ingestion of normally innocuous peanut protein. Cross-linking of peanut-specific IgE (sIgE) bound to high affinity IgE receptors on mast cells and basophils triggers immediate degranulation. Subsequent release of a diverse array of inflammatory mediators results in severe allergic symptoms such as hives, wheezing, vomiting and, in severe cases, anaphylactic shock. Release of these mediators also initiates Type 2 T-helper cell (Th2) cytokine release, which results in eosinophil infiltration and creates a vicious cycle of chronic allergic inflammation. Like other forms of allergy immunotherapy, OIT to peanut involves a slow up-dosing of exposure to allergen, in this case peanut, over time to desensitize or increase the threshold of reactivity to peanut. Once reaching a target level of peanut protein, subjects are continued on a maintenance dose of peanut protein to maintain desensitization. Although many subjects on a maintenance dose of peanut protein have demonstrated desensitization to peanut (ie, the ability to tolerate a level of exposure to peanut without an allergic reaction), up to 80% of subjects exhibit related adverse events (AEs) during OIT, with 42% experiencing systemic reactions and 49% experiencing gastrointestinal (GI) symptoms; the majority of these are mild and decline with prolonged treatment (Virkud, 2016). Up to 20% of subjects, however, are unable to complete the up-dosing regimen due to side effects, which are primarily GI related. An additional issue with current OIT is its limited ability to induce clinical tolerance when subjects are taken off daily peanut intake (Vickery, 2014). In many of the studies with peanut OIT, despite years of immunotherapy, subjects never achieve tolerance and are re-sensitized within weeks of halting daily peanut intake, with a small percentage ($\sim 10\%$) maintaining a sustained unresponsiveness even after 3 months off OIT.

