10.4. Recording and Reporting Adverse Events

10.4.1. Adverse Events

The investigator (or designee) will record all AEs that occur from the time the informed consent/assent is signed until the end of study. However, allergic reactions to the DBPCFC during the Screening phase, at endpoint challenges (at visits 16, 22, and 25), during AR101 in-clinic dosing visits, and daily home dosing will be recorded as allergic signs and symptoms since they are anticipated to allergen. Refer to the study reference manual for the procedures to be followed.

Information on follow-up for AEs is provided in Section 10.4.6. Laboratory and vital signs abnormalities are to be recorded as AEs as outlined in Section 10.4.5.

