1.2.2. Secondary Objectives

- To assess whether dupilumab as adjunct to AR101 compared to placebo as adjunct to AR101 improves desensitization at the completion of up-dosing, defined as an increase in the cumulative tolerated dose (log transformed) of peanut protein during a post up-dosing DBPCFC at visit 16
- To assess whether dupilumab as (indefinite [continuously]) adjunct to AR101 compared to placebo maintains desensitization, defined as an increase in the proportion of subjects who pass a post maintenance DBPCFC at visit 22
- To assess whether dupilumab as (limited [previously]) adjunct to AR101 compared to placebo maintains desensitization, defined as an increase in the proportion of subjects who pass a post maintenance DBPCFC at visit 22
- To evaluate the safety and tolerability of dupilumab as adjunct to AR101 compared to placebo
- To assess the effect of dupilumab (compared to placebo) as adjunct to AR101 on the change in peanut-specific IgE, IgG, IgG4, peanut-specific IgG4/IgE ratio, and peanut-specific IgG/IgE ratio

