4.5.3. Exploratory Efficacy Variable (s)

Exploratory efficacy endpoints include:

- Proportion of subjects who "pass" an end of study DBPCFC with 2044 mg (cumulative) peanut protein at visit 25
- Change from baseline in total FAQLQ score at visit 16, visit 22, and visit 25 for different types of FAQLQ form
- Proportion of subjects experiencing none, mild, moderate, severe or higher allergic symptoms by treatment group during DBPCFCs of peanut protein at visit 16 and visit 22
- Change and percent change from baseline to visit 16, visit 22 and visit 25 in peanutspecific IgG
- Change and percent change from baseline to visit 16, visit 22 and visit 25 in peanutspecific IgG4
- Change and percent change from baseline to visit 16, visit 22 and visit 25 in total IgE
- Change from baseline to visit 16, visit 22 and visit 25 in log- transformed peanut-specific IgG4/ peanut-specific IgE ratio
- Change from baseline to visit 16, visit 22 and visit 25 in log- transformed peanut-specific IgG/ peanut-specific IgE ratio
- Change from baseline to visit 16, visit 22 and visit 25 in peanut-specific IgE
- Change from baseline to visit 16, visit 22 and visit 25 in log- transformed peanutspecific IgE/total IgE ratio
- Change and percent change from baseline to visit 16, visit 22 and visit 25 in Ara h1 sIgE, Ara h1 sIgG4, Ara h2 sIgE, Ara h2 sIgG4, Ara h3 sIgE, Ara h3 sIgG4
- Change from baseline to visit 16, visit 22 and visit 25 in log- transformed Ara h1-specific IgG4/ Ara h1-specific IgE ratio
- Change from baseline to visit 16, visit 22 and visit 25 in log- transformed Ara h2-specific IgG4/ Ara h2-specific IgE ratio
- Change from baseline to visit 16, visit 22 and visit 25 in log- transformed Ara h3-specific IgG4/ Ara h3-specific IgE ratio

- Change from baseline to visit 16, visit 22 and visit 25 in Ara h1-specific IgE/ peanutspecific IgE ratio
- Change from baseline to visit 16, visit 22 and visit 25 in Ara h2-specific IgE/ peanut-specific IgE ratio
- Change from baseline to visit 16, visit 22 and visit 25 in Ara h3-specific IgE/ peanut-specific IgE ratio
- Change and percent change from baseline to visit 16, visit 22 and visit 25 in basophil sensitivity to peanut allergen, as measured by EC50, which is the concentration of peanut protein required to achieve 50% of maximal basophil activation
- Change and percent change from baseline to visit 16, visit 22 and visit 25 in the frequency of peanut-specific T cell subsets (e.g. Th2A cell)

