4.6. Safety Variables

4.6.1. Adverse Events and Serious Adverse Events

An **Adverse Event** (AE) is any untoward medical occurrence in a subject administered a study drug, which may or may not have a causal relationship with the study drug. Therefore, an AE is any unfavorable and unintended sign (including abnormal laboratory finding), symptom, or disease, which is temporally associated with the use of a study drug, whether or not considered related to the study drug.

An AE also includes any worsening (i.e., any clinically significant change in frequency and/or intensity) of a pre-existing condition that is temporally associated with the use of the study drug.

A Serious Adverse Event is any untoward medical occurrence that at any dose results in death; is life-threatening; requires in-patient hospitalization or prolongation of existing hospitalization; results in persistent or significant disability/ incapacity; is a congenital anomaly/ birth defect; or is an important medical event.

Adverse events and serious adverse events will be collected from the time of informed consent/assent is signed until the end of the study. However, allergic reactions to the DBPCFC during the Screening phase, at endpoint challenges (at visits 16, 22, and 25), during AR101 inclinic dosing visits, and daily home dosing will be recorded as allergic signs and symptoms since they are anticipated to allergen challenge.

All adverse events are to be coded to a "Preferred Term (PT)", "High Level Term (HLT)" and associated primary "System Organ Class (SOC)" according to the Medical Dictionary for Regulatory Activities (MedDRA, the latest available version).

Abnormal laboratory or vital signs will be graded according to the FDA September 2007. The criteria for determining whether an abnormal objective test finding should be reported as an AE include:

- Test result is associated with accompanying symptoms, and/or
- Test result requires additional diagnostic testing or medical/surgical intervention, and/or

Regeneron Pharmaceuticals, Inc. Statistical Analysis Plan

• Test result leads to a change in dosing (outside of protocol-stipulated dose adjustments), or discontinuation from the study, significant additional concomitant drug treatment, or other therapy

The pre-treatment and treatment-emergent periods are defined as following:

- The pre-treatment period is defined as the time from signing the ICF to before the first dose of study drug.

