5.7. Analysis of Safety Data

The analysis of safety and tolerability will be performed on the SAF and SAF-maintenance for each study period, as defined in Section 3.3.

The safety analysis will be based on the reported AEs, clinical laboratory evaluations, physical examination, vital signs and spirometry.

Thresholds for treatment-emergent Potential Clinically Significant Values (PCSV) in laboratory variables and vital signs are defined in Section 10.3. Treatment-emergent PCSV is any PCSV developed or worsened in severity compared to the baseline during the treatment and follow-up period.

The time interval to detect any event or abnormality is between the first injection of study medication and EOS.

The summary of safety results will be presented for each study period by treatment received in the corresponding period. For safety variables/summaries involving baseline values, e.g., absolute change from baseline or shift table, study period specific baselines will be used. Summaries for pre-dosing period and up-dosing period will use the study baseline (i.e., the latest available valid measurement prior to the first dose of study drug in the study). Summaries for maintenance period and follow-up period will use study baseline and visit 16 baseline (i.e., the last available valid measurement prior to the first dose of study drug in the maintenance period), respectively.

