5.7.1. Adverse Events

The number and proportion of subjects reporting TEAEs will be summarized for pre-dosing period, up-dosing period, maintenance period and follow-up period separately, as described in Section 3.3.

AE incidence tables will be presented by treatment group for the SAF and SAF-maintenance as well as subgroups. Summary of TEAEs will present the number (n) and percentage (%) of subjects experiencing an TEAE by SOC, and PT, sorted by decreasing frequency of SOC and PT for the dupilumab treatment group in the pre-dosing period, dupilumab plus AR101 treatment group in the up-dosing period, and continuously on dupilumab plus AR101 treatment group in the maintenance period. Multiple occurrences of AEs of the same PT (or SOC) in the same subject will be counted only once for that PT (or SOC). For AE tables presenting severity, the worst severity will be chosen for subjects with multiple instances of the same event. The denominator for computation of percentage is the number of subjects in each treatment group for the corresponding analysis period as specified in Section 3.3.

An overall summary of TEAEs will be provided with number and proportions of subjects with any:

- TEAE
- Serious TEAE
- TEAE of special interest (AESI)

- TEAE/Serious TEAE leading to death
- TEAE/Serious TEAE leading to permanent treatment discontinuation
- TEAE/Serious TEAE of injection site reaction
- Study drug related TEAE/serious TEAE

Detailed summaries of TEAEs will include:

- TEAEs
 - TEAEs by SOC/PT
 - TEAEs by SOC/HLT/PT
 - TEAEs by PT
 - TEAEs by SOC/PT with incidence of $PT \ge 5\%$ in any treatment group
 - TEAEs by severity and by SOC/PT
 - Severe TEAEs by SOC/PT
 - TEAEs related to dupilumab/placebo as assessed by the investigator by SOC/PT
 - TEAEs related to AR101 as assessed by the investigator by SOC/PT
 - Severe TEAEs related to dupilumab/placebo as assessed by the investigator by SOC/PT
 - Severe TEAEs related to AR101 as assessed by the investigator by SOC/PT
 - TEAE of special interest
- Serious TEAEs:
 - Serious TEAEs by SOC/PT
 - Serious TEAEs related to dupilumab/placebo as assessed by the investigator by SOC/PT
 - Serious TEAEs related to AR101 as assessed by the investigator by SOC/PT
- TEAEs leading to permanent discontinuation of study treatment by SOC/PT
- Death by SOC/PT

Number and proportion of subjects reporting pre-treatment adverse events will be tabulated by SOC and PT.

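### Allergic reactions at AR101 dosing are recorded outside the AE data and have no severity-graded summary by arm, so the AR101-related TEAE tables understate non-serious dosing reactions

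*Protocol*

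**What the plan says.** Protocol 10.4.1 has investigators record all AEs from consent to end of study, then carves out allergic reactions at the food challenges, at in-clinic AR101 dosing and at home dosing, which "will be recorded as allergic signs and symptoms since they are anticipated to allergen". SAP 4.6.1 carries the same exception: reactions at in-clinic visits and "daily home dosing will be recorded as allergic signs and symptoms since they are anticipated to allergen challenge".

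SAP 5.7 names the data behind the safety analysis: "The safety analysis will be based on the reported AEs, clinical laboratory evaluations, physical examination, vital signs and spirometry". The allergic-signs-and-symptoms record is not in that list. SAP 5.7.1 then plans "TEAEs related to AR101 as assessed by the investigator by SOC/PT", with further tables restricted to severe and to serious events.

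The one planned none, mild, moderate, severe-or-higher tabulation is exploratory and concerns "allergic symptoms by treatment group during DBPCFCs of peanut protein at visit 16 and visit 22" (SAP 4.5.3; the list in SAP 1.2.3 adds visit 25).

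Tolerability remains a secondary objective in SAP 1.2.2: "To evaluate the safety and tolerability of dupilumab as adjunct to AR101 compared to placebo". Protocol 3.2.1 says differences in safety and tolerability will be assessed by comparing AEs and drop-out between the treatments.

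**The concern.** Reactions to the peanut dose are the main expected harm of AR101, and better tolerability of up-dosing is one of the effects the trial hopes to show (Protocol 1). A table headed as AR101-related TEAEs would normally be read as the account of that harm. Here a recording rule moves most non-serious dosing reactions into another dataset, and the SAP plans no graded summary of that dataset outside the challenges. A reader of the report could take the tabulated rate as the AR101 reaction rate in each arm, and the arm comparison promised in Protocol 3.2.1 would be made on AEs that leave these reactions out.

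**Working it through.** The plan states no figure on this point, so there is nothing to reproduce. The check is a trace of where a dosing reaction goes.

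**Step 1. Which reactions leave the TEAE tables.** Protocol 10.4.1 removes dosing reactions from AE recording. Protocol 10.4.2 requires every SAE to be reported, with no exemption for allergic reactions. Protocol 10.4.3 keeps the AESIs reportable: anaphylaxis, systemic or extensive hypersensitivity, and GI AEs that disrupt dosing for a prolonged period. The gap is therefore non-serious reactions that are not AESIs, which means mainly mild and moderate ones.

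**Step 2. What the SAP summarises by arm outside the challenges.**

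| Source | Coverage | Limit |
|---|---|---|
| Diary symptom-days: any symptom, score 7 or more, by category (SAP 4.5.3, 5.12) | Up-dosing, challenge days excluded | Exploratory and descriptive; self-rated 1-10, not CoFAR; no maintenance analysis; replaced secondary endpoints dropped for low entry compliance (SAP 1.2.3) |
| Anaphylaxis: counts, maximum severity, SAE status, epinephrine (SAP 5.7.2) | Every period and the challenges | Anaphylactic reactions only |
| Epinephrine and short-term systemic steroid use; time to first rescue (SAP 5.3) | IDED, up-dosing and maintenance; rescue curves for each period | Treated reactions only |
| GI AESI search (SAP 10.5) | GI events with prolonged dosing disruption | Needs a coded GI preferred term, so a GI reaction held only as an allergic symptom may be missed |

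The first of the two diary calculations in SAP 4.5.3 divides symptom days by all days of the up-dosing treatment, so a day with no entry counts as symptom-free. The second divides by days with an entry.

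**Step 3. What has no summary.** No table shows, by arm, how many subjects reacted at the IDED, at in-clinic up-dosing or at home dosing, or how severely. A moderate reaction that leads to a dose reduction under Protocol 6.1.1.2, without anaphylaxis, epinephrine or steroids, can reach the report only through the diary.

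**Step 4. Scale of time covered.** AR101 is taken for 24 to 36 weeks of up-dosing and 24 weeks of maintenance.
- Shortest: (24 + 24) × 7 = 336 dosing days.
- Longest: (36 + 24) × 7 = 420 dosing days.
- Graded table: peanut challenge days at visits 16 and 22, plus visit 25 if SAP 1.2.3 is followed, so at most 3. Visit 25 comes after AR101 has stopped.

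This compares days observed. It is not an estimate of reactions missed.

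**Step 5. Consistency.** Four places sit badly with Protocol 10.4.1:
- Section 3.2.1 relies on AEs to compare tolerability.
- Section 6.1.1.2 has the next-day call ask about AEs, allergic symptoms included, and help enter them in the diary.
- Section 10.5.1 gives a CoFAR grade to allergic reactions within AE severity.
- Section 11.4.4.1 tabulates TEAEs by that severity scale.

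**The case against.** The strongest reply is that the SAP does not ignore dosing reactions. It summarises diary symptom-days by treatment group in up-dosing, anaphylaxis in each period, and epinephrine, steroid and rescue use outside the challenges. SAEs and AESIs stay in the safety data. Tolerability also has other measures by arm: reaching 300 mg/day and the time to reach it, discontinuations by reason, and TEAEs leading to discontinuation. All of this stands. A reader might infer that reactions are tabulated only for food challenges, or are never compared between arms during up-dosing. The documents do not support either reading.

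A reader might also size the gap from the Protocol Introduction, which says that "up to 80% of subjects exhibit related adverse events (AEs) during OIT". Multiplying, 0.80 × 52 gives about 42 placebo-arm subjects. That does not follow. The rate is a literature background figure for OIT, nothing in the documents says what share of those events arises at dosing, and some would still be captured as SAEs, AESIs or rescue use.

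It can further be said that some sites may report dosing reactions as AEs anyway, since the next-day call and Protocol 10.5.1 point that way, and that Protocol 10.4.1 defers procedure to a study reference manual that is not supplied. This is fair, and it limits what can be said about practice. It does not rescue the plan as written: uneven AE reporting of dosing reactions would make the tables harder to interpret.

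Finally, home reactions may exist only in the diary, on a 1-10 scale. That stands, and it limits the fix.

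**Conclusion.** The point holds in a bounded form. If the recording rule is followed, the AR101-related TEAE tables understate non-serious dosing reactions, and mild and moderate reactions at the IDED, in-clinic up-dosing and home dosing have no severity-graded summary by arm. The table of serious AR101-related TEAEs is not affected in the same way, because SAEs remain reportable. The table of severe ones is affected only for severe reactions that are neither serious nor an AESI.

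The size of the understatement cannot be calculated from the documents, and neither can its effect on a difference between arms. The conclusion rests on two assumptions: that sites apply Protocol 10.4.1 as written, and that the separate record exists in usable form. Protocol 6.1.2 supports the second, since it says dosing allergic symptoms are captured throughout. For a phase 2 trial with tolerability as a secondary objective, the summary should be added before database lock. The primary efficacy analysis is not touched.

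**What to change.** In SAP 5.7.1, add a separate summary, by arm and study period, of the recorded allergic signs and symptoms at the IDED, at in-clinic up-dosing and at home dosing:
- subjects with any reaction;
- worst CoFAR grade, where the site graded the reaction;
- reactions per AR101 dosing day, with the denominator defined (the exposure duration in SAP 5.5.2 ignores interruptions).

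Match these records to the AE data, and count a reaction once if it was also reported as an AE, SAE or AESI. Footnote the AR101-related TEAE tables to say that reactions recorded under the Protocol 10.4.1 exception appear in this summary and not in the TEAE rows.

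Reconcile Protocol 3.2.1, 6.1.1.2, 10.5.1 and 11.4.4.1 with 10.4.1. Ask the sponsor to confirm where home-dosing reactions are stored and whether they carry a grade.

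The cost is one derivation and one table set, with no new data collection or subject burden. The limit is that home reactions held only in the diary may have no CoFAR grade and would share the diary's low compliance. Show them separately instead of assigning a grade.

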10.4.2. Serious Adverse Events

All SAEs, regardless of assessment of causal relationship to study drug, must be reported to the sponsor (or designee) within 24 hours. Refer to the study reference manual for the procedure to be followed.

Information not available at the time of the initial report must be documented in a follow-up report. Substantiating data such as relevant hospital or medical records and diagnostic test reports may also be requested. In the event the investigator is informed of an SAE after the subject completes the study (ie, the follow-up period), the following will apply:

- If the subject is an early termination from the study, SAE with an onset within 12 weeks of last study drug administration will be reported to the sponsor. The investigator should make every effort to obtain follow-up information on the outcome until the event is considered chronic and/or stable.
- For SAEs with an onset day greater than 12 weeks from the last study drug administration, only those deemed by the investigator to be drug-related SAEs will be reported to the sponsor. The investigator should make every effort to obtain follow-up information on the outcome of a drug-related SAE until the event is considered chronic and/or stable.

10.4.3. Other Events that Require Accelerated Reporting to Sponsor

The following events also require reporting to the sponsor (or designee) within 24 hours of learning of the event:

- **Pregnancy:** Although pregnancy is not considered an AE, it is the responsibility of the investigator to report to the sponsor (or designee), within 24 hours of identification, any pregnancy occurring in a female study subject, during the study or within 12 weeks of the last dose of study drug. Any complication of pregnancy affecting a female study subject, and/or fetus and/or newborn that meets the SAE criteria must be reported as an SAE. Outcome for all pregnancies should be reported to the sponsor.
- Adverse Events of Special Interest: All AESI, serious and non-serious, must be reported within 24 hours of identification using the same reporting process as for SAE reporting, per Section 10.4.2.

Adverse events of special interest for dupilumab in this study include the following:

- Anaphylactic reactions
- Systemic or extensive hypersensitivity reactions
- Helminthic infections
- Conjunctivitis (any type or etiology), keratitis, or blepharitis (for all these AEs only events that are severe or serious or lasting \geq 4 weeks will be reported as AESIs)

Adverse events of special interest for AR101 in this study include:

- Anaphylactic reactions
- Gastrointestinal AEs resulting in prolonged disruption of dosing

Refer to the study manual for the procedures to be followed.

